Interventions. The first CM group in Phase 1 will follow the existing Emory Compassion Meditation Protocol. This well-developed protocol has been used extensively with non-clinical populations but some initial refinement will be done to assure that the material is accessible to veterans. The subsequent groups will be delivered using the protocol version developed with the prior group until a well-received protocol has been established. The initial relaxation group will follow [name] protocol with minor modification to match the timeline of the CM protocol (i.e., extending sessions from 90 minutes to 2 hours and providing similar amounts of homework) and modality of administration (group rather than individual). If necessary, this protocol will be refined based on participant feedback as well. The final versions of the protocols will be employed in Phase 2. Both types of groups will be conducted in person by a trained licensed clinical psychologist in eight 2-hour sessions.

Randomization. There is no randomization in Phase 1. In Phase 2, groups will be randomized in a 1:1 allocation ratio to CM or Relaxation Training; no stratification will be used. The assessor will be kept blind to treatment condition. Random assignment of groups to study conditions will be conducted by study statistician, [name], after the groups have been formed. Prior to enrollment, the study statistician will write a program in SPSS (IBM Software Group. SPSS User' Guide, Version 21. Chicago, Il, 2013) to create a list of subject identification numbers with randomized treatment assignments (2 CM and 2 relaxation groups), which will be held by the unblended project coordinator during the trial. Variable blocked randomization will be used with random block size (4 or 6). Separate lists (up to 4) of replacement subject identification numbers will also be created so that replacement subjects are assigned the same treatment as subjects they are replacing. Subjects will be randomized to study treatment group in a 1:1 ratio.

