9.6 Data Analyses

Although majority of data will be quantitative, some qualitative data also will be collected. [name] has experience with qualitative coding and analyses. [name] also has been added to the study team for her experience with qualitative interviewing, coding and analyses. We will analyze qualitative data using atlas.ti, a qualitative data analysis software package. Qualitative data analysis starts with coding, a process in which quotes are marked and labeled. The labeled quotes are then sorted and grouped, so that categories, then concepts, then themes can be developed. As is often standard practice for qualitative data analysis, analysis will be concurrent with data acquisition.

Quantitative data will be analyzed using SPSS version 18. These data will be examined initially for missing values. The primary aims of our data analytic strategy in phase 1 will be directed toward the development of CM and collection of data that will inform modification of the interventions. In phase 2 it will be directed toward examining the feasibility of CM. We would like to emphasize that, although we aim to estimate effect sizes to assist in future power calculations, this is not our major focus. Recent work by Kraemer (2006) has highlighted important limitations of this aim due to the large standard error surrounding the pilot study effect size. As a result, we will focus our analyses on a feasibility of conducting a larger CM study and report our findings with this limitation in mind. Our goal is to collect important data regarding the development of CM protocols, our ability to implement recruitment strategies, and the feasibility of the treatment and measurements. Information derived from our research will lead

to better-designed full-scale studies and informs decisions regarding whether it is worthwhile to commit additional resources to future CM treatment development. Due to our small sample size our statistical analytical findings should be interpreted with caution.

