For quantitative data, descriptive statistics will be used to summarize the variables as well as to detect outliers and data entry errors. When applicable, normality of the distribution will be examined for outcome variables with a normal probability plot. HRV measures will be generated from heart rate data per the recommendations of the Task Force of the European Society of Cardiology and the North American Society of Pacing and Electrophysiology (Task Force, 1996). Chi- squares and Analysis of Variance will be used to assess the effectiveness of the randomization procedures by comparing participants in each treatment condition on baseline variables. Although there are important limitations associated with the analysis of our phase 2 data, we do propose to conduct limited statistical analyses. First, keeping in mind the theoretical and practical issues reviewed above, all analyses will be considered preliminary. We will calculate an estimated effect size for our primary outcome, though it will be interpreted with caution, and in the context of the 95% confidence interval that surrounds it. It will also be interpreted within the context of other important information such as the clinical significance of study findings, and existing data from prior relevant research studies.

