Primary analyses will assess whether CM is superior to Relaxation. The two groups will be compared on CAPS, BSI, SDS and Philadelphia Mindfulness Scale using analysis of variance. We are also particularly interested in evaluation of patterns of missing data, dropout rates, distributional properties of variables, and correlations among measures. Missing data will be examined to assess randomness. The pattern of missing data will be examined according to the procedure recommended by Little and Rubin (1987), which includes comparing group differences in the primary outcomes of subjects with versus without missing data. We will test whether the drop-outs are random or systematic by comparing the drop-outs with the study completers on the baseline data. An absence of significant differences would support the random nature of drop- outs. Dropout rate will be compared between the groups using chi-square analysis. Given the limited sample size, multiple linear regression may be used carefully to examine whether group assignment predicts PTSD symptom severity at the follow-up assessment while controlling for initial values. Other potential covariates will include baseline demographic or clinical variables (e.g., concomitant medication use) that are not equivalent between the two treatment groups. Effect size for the difference between groups will be calculated according to procedures described by Cohen (1988). We will also explore the effect of patterns of missing data using Mixed Effects models (random regression models). We will perform sensitivity analyses for the impact that potentially informative missing data and dropout may have on the analyses. The mixed effects framework is robust with respect to drop-out and missing data, unless the drop-out mechanism or cause of missing is informative. We will use pattern-mixture models to assess if there is bias due to drop out or missing data.

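### The Phase 2 analysis has no therapy-group term, so any positive within-group correlation makes its 95% CI too narrow for inference to other therapy groups; the unit of randomisation is also stated two ways

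*Combined protocol and SAP*

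**What the plan says.** Section 9.2 plans four Phase 2 groups, two of compassion meditation (CM) and two of relaxation, with 6 to 12 people each and about 40 in all. Treatment is eight two-hour group sessions (Sections 3 and 5.1). CAPS-5 is the primary outcome (9.5.1).

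Section 9.6 states the aim: "Primary analyses will assess whether CM is superior to Relaxation". The method follows: "The two groups will be compared on CAPS, BSI, SDS and Philadelphia Mindfulness Scale using analysis of variance". A Cohen effect size is to be read "in the context of the 95% confidence interval that surrounds it".

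Two further models appear. One is optional and adjusts for initial values: "multiple linear regression may be used carefully to examine whether group assignment predicts PTSD symptom severity". The other concerns missing data: "We will also explore the effect of patterns of missing data using Mixed Effects models (random regression models". Neither includes therapy group. No section mentions clustering, an ICC or a design effect.

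The plan also limits its own claims. Section 9.6 says that "although we aim to estimate effect sizes to assist in future power calculations, this is not our major focus", and that "Due to our small sample size our statistical analytical findings should be interpreted with caution".

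On allocation, Section 3 says "In Phase 2, groups will be randomized in a 1:1 allocation ratio to CM or Relaxation Training". The same paragraph also describes a subject-level scheme, set out under the working.

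**The concern.** People who share eight group sessions and a therapist may have correlated outcomes. An analysis that treats them as independent then understates the standard error.

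This matters because preliminary effect-size estimates are a primary objective (Section 1.1) and are meant to inform the planning of later trials, whose therapy groups will be different ones. The confidence interval is the plan's own guard against over-reading a pilot estimate, and an interval that is too narrow weakens that guard.

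The unit of randomisation decides how far the problem reaches. It also decides what staff actually do, and they cannot carry out both versions.

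**Working it through.** **Group size.** Phase 1 plans 60 people in 6 groups, so 60/6 = 10 per group. Four groups of 10 give 40, which reproduces the Phase 2 figure. The stated range of 6 to 12 gives 24 to 48.

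**Inputs.** Two groups per arm of m = 10 each, and total variance 1, so results are in SD units. The documents give no ICC; 0 to 0.10 is assumed.

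**Formulas.**
- Design effect: DE = 1 + (m − 1) × ICC.
- True SE of the difference: √(DE × 2/(2m)).
- Expected variance estimate in the planned ANOVA: [4(m − 1)(1 − ICC) + 2 × DE]/(4m − 2).
- Half-width at ICC 0: t(0.975, 38) × √(2/20) = 2.024 × 0.316 = 0.640. At other ICCs this is multiplied by √DE.

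Example at ICC 0.05: DE = 1 + 9 × 0.05 = 1.45 and the true SE is √(1.45 × 0.1) = 0.381. The expected ANOVA variance is (36 × 0.95 + 2.90)/38 = 0.976, so the naive SE is √0.0976 = 0.312. The ratio is 1.22.

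Coverage and type I error come from simulation of the planned unadjusted ANOVA (200,000 replicates per setting; repeat runs agreed to within about 0.2 percentage points).

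| Assumed ICC | DE | True SE / naive SE | Coverage of nominal 95% CI | Type I error at nominal 5% | Half-width × √DE (SD) |
|---|---|---|---|---|---|
| 0 | 1.00 | 1.00 | 95.0% | 5.0% | 0.640 |
| 0.01 | 1.09 | 1.05 | 94.0% | 6.0% | 0.668 |
| 0.02 | 1.18 | 1.09 | 92.9% | 7.1% | 0.695 |
| 0.05 | 1.45 | 1.22 | 89.5% | 10.5% | 0.771 |
| 0.10 | 1.90 | 1.41 | 84.0% | 16.0% | 0.882 |

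**Variations.**
- From groups of 6 to groups of 12, coverage runs from about 94.5 to 93.7% at ICC 0.01, 92.0 to 88.1% at 0.05, and 88.8 to 81.7% at 0.10.
- With 8 analysed per group (20% dropout, assumed), coverage at those three ICCs is 94.2, 90.7 and 86.2%.
- Adjusting for baseline does not remove the effect. With groups of 10, an assumed baseline correlation of 0.5 and the same ICCs in the residual, coverage is 94.0, 89.5 and 84.4%.

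**Does inflating the SE by √DE help?** With equal groups of 10 and the assumed ICC equal to the true one, coverage is 95.0, 95.0, 94.7 and 94.5% at ICC 0, 0.01, 0.05 and 0.10. If the assumed ICC is too low, coverage still falls short: about 90.8% when 0.05 is assumed and 0.10 is true, and about 87.9% when 0.10 is assumed and 0.20 is true. With one group of 6 and one of 12 in each arm, using the mean group size at a true ICC of 0.10 gives 93.6%.

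**Unit of randomisation, side by side.**
- Groups: two sentences in Section 3 and one in Section 9.2 assign groups to conditions. Section 3 adds that this happens once the groups exist.
- Subjects: Section 3 also sets out a list of subject numbers prepared before enrolment, blocks of 4 or 6, replacement numbers that inherit the replaced person's treatment, and a closing sentence that randomises subjects 1:1. Four groups cannot fill a block of 6.
- Either: the Précis speaks of random assignment to four groups. Section 6.2.2 places randomisation within a month of baseline and a week of group start, which fits both versions.

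**Allocations if groups are the unit.** If all four are allocated together, two to each arm, there are C(4,2) = 6 allocations and the smallest two-sided randomisation p-value is 2/6 = 0.33. If they are allocated in two pairs, there are 2 × 2 = 4 allocations and the smallest p-value is 2/4 = 0.50. The documents do not say which applies.

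**The case against.** The strongest reply is that the plan already guards against over-reading. Section 9.6 notes the small sample and the large standard error of a pilot effect size, calls all analyses preliminary, and says effect size is not the main focus. No stopping rule or stated decision threshold uses this interval. At ICC 0.01 to 0.02 the half-width grows by only 0.03 to 0.06 SD on 0.64, and the larger shortfalls rest on assumed ICCs. All of this stands and limits the consequence. It does not remove the point: a reader who heeds those cautions turns to the confidence interval, which is the quantity affected.

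A reader might also infer more than the documents support:

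- **That the naive interval is sound for these four groups in any case.** That holds only if subjects are randomised. If formed groups are randomised, group differences are confounded with arm, and the interval is also too narrow within the trial.
- **That the timing in Section 6.2.2 settles the unit as subjects.** It does not discriminate. The block of 6 and the subject list do point to subjects, but the group sentences remain.
- **That 0.33 is the trial's smallest attainable p-value.** That assumes group randomisation with all four groups allocated together.
- **That the superiority comparison must be dropped** because Section 9.1 describes the study as developmental. Section 9.6 already calls these analyses limited and preliminary. Rewording would align the sections, but giving up the test is largely a preference.

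**Conclusion.** The point holds. The planned ANOVA, effect size and 95% interval omit therapy group. For inference to other therapy groups, any positive within-group correlation in CAPS-5 makes the interval too narrow and the superiority p-value too small. If formed groups are randomised, the same is true within this trial.

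The direction is certain for any positive ICC; the size is not known. At ICC 0 there is no shortfall and at 0.01 it is about one percentage point. With groups of 10 it is about 5.5 points at 0.05 and 11 points at 0.10. These figures assume two equal groups per arm and the same ICC in both arms.

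The contradiction over the unit of randomisation does not depend on any assumed figure and needs correcting in its own right. The whole point is worth fixing, but it does not undermine the trial's feasibility aims.

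**What to change.** 1. **Section 9.6.** Report the CAPS-5 difference and effect size with the 95% interval at assumed ICCs of 0, 0.01, 0.05 and 0.10 (and 0.20 if wished), multiplying the SE by √(1 + (m − 1) × ICC), where m is the mean number analysed per group. Call this a sensitivity display, not a correction: it holds nominal coverage only approximately, and only if the assumed ICC is right and group sizes are similar. Beside the small-sample caution, add wording such as: *Each arm is delivered in only two therapy groups, so the between-group variance cannot be estimated reliably; intervals are shown over a range of assumed ICCs.*

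2. **Précis, Section 3 and Section 9.2.** State one unit of randomisation. If subjects, correct the three group-assignment sentences (two in Section 3, one in 9.2). If groups, delete the subject list, block sizes, replacement lists and the sentence randomising subjects. Then state how the four groups are allocated and that very few allocations are possible.

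3. **Optional.** Describe the superiority comparison in 9.6 as preliminary estimation, in line with Section 9.1.

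**Cost.** Protocol wording and a few lines of analysis, with no extra participants. With groups of 10 the interval is about 4% wider at ICC 0.01 (√1.09 = 1.04), 20% at 0.05 (√1.45 = 1.20) and 38% at 0.10 (√1.90 = 1.38). Readers see several intervals instead of one.

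### Section 9.6 reads a non-significant baseline comparison of drop-outs and completers as support for random drop-out; about 40 people cannot show this, and baseline data could not show it at any sample size (minor)

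*Combined protocol and SAP*

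**What the plan says.** Section 9.6 sets out this check on attrition: "We will test whether the drop-outs are random or systematic by comparing the drop-outs with the study completers on the baseline data". It then gives the reading of a null result: "An absence of significant differences would support the random nature of" drop-outs. A second check, on the pattern of missing data, involves "comparing group differences in the primary outcomes of subjects with versus without missing data".

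For the treatment comparison, the same section says: "The two groups will be compared on CAPS, BSI, SDS and Philadelphia Mindfulness Scale using analysis of variance". Adjustment for the initial value is optional: "multiple linear regression may be used carefully to examine whether group assignment predicts PTSD symptom severity" at follow-up. Section 9.3 describes an intent-to-treat analysis that includes all subjects, without saying how someone with no post-treatment score is included.

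Section 9.6 goes further on missing data than these checks alone. It plans mixed models and states their condition: "The mixed effects framework is robust with respect to drop-out and missing data, unless the drop-out mechanism or cause of missing is informative". It promises sensitivity analyses for informative drop-out and adds: "We will use pattern-mixture models to assess if there is bias due to drop out or missing data". Sections 6.2.5 and 8 ask people who leave treatment early to complete the remaining assessments. On the standing of the Phase 2 results, section 9.6 says that, "keeping in mind the theoretical and practical issues reviewed above, all analyses will be considered preliminary".

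**The concern.** A non-significant test is weak evidence of no difference unless the study could have detected a difference that matters. Phase 2 is small, and the drop-out group will be a fraction of it.

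There is also a problem that more participants would not solve. The drop-out that biases a treatment comparison is often related to how people respond after baseline. Drop-outs and completers can look alike at entry and still differ in response. The second check does not fill the gap for everyone: in the Phase 2 schedule (section 6.1) CAPS-5 is collected only at baseline and post-treatment, so a person without the second value has only a baseline score to compare.

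Section 9.6 names missing-data patterns and drop-out rates as a particular interest, and says that the results should inform larger studies. A null baseline test reported as reassurance could be carried into the next trial's design although it says little either way.

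**Working it through.** **Inputs from the document.** Phase 2 has about 40 people in 4 groups of 6–12 (section 9.2), so 4 × 6 = 24 to 4 × 12 = 48; 40 corresponds to 10 per group. Sections 6.1 and 6.2.2 list about 12 Phase 2 baseline measures: CAPS-5, BSI, SDS, SWLS, PHLMS, SCS-R, SCS-SF, four PROMIS scores and heart rate variability. Demographics, DES and MoCA come on top. The plan gives no power figure for this test, so there is none to reproduce.

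**Assumptions.** Drop-out of 10–40% (no rate is stated), two-sided 0.05, equal variances, independent participants. Clustering by therapy group is ignored.

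**Step 1: one baseline variable, N = 40.** With k drop-outs, the standard error of the difference in SD units is √(1/k + 1/(40−k)). Power comes from the noncentral t with 38 degrees of freedom and noncentrality d/SE. The 95% half-width is 2.024 × SE.

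| Drop-outs k | SE (SD) | Power, d = 0.5 | Power, d = 0.8 | d for 80% power | 95% half-width (SD) |
|---|---|---|---|---|---|
| 4 | 0.527 | 15% | 32% | 1.52 | 1.07 |
| 8 | 0.395 | 23% | 51% | 1.14 | 0.80 |
| 12 | 0.345 | 29% | 62% | 0.99 | 0.70 |
| 16 | 0.323 | 33% | 68% | 0.93 | 0.65 |

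A 0.5 SD difference on that variable would be missed in 67–85% of trials. An observed difference of zero would still be compatible with a true difference of 0.65–1.07 SD. Over the same drop-out range, power at 0.5 SD is 10–21% for N = 24 and 18–38% for N = 48. Reaching 80% power at 0.5 SD would take about 349, 197, 150 or 132 people in total at 10%, 20%, 30% or 40% drop-out (normal approximation).

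**Step 2: drop-out driven by response.** In an illustrative simulation (N = 40, participants with worse outcomes more likely to leave the CM arm), a single baseline test was non-significant in 90–95% of trials, for baseline–outcome correlations from 0.5 down to 0. The completer comparison was biased by about 0.29 SD in favour of CM. The bias was the same among trials where the baseline test was non-significant, so the test gave no warning.

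**Step 3: twelve variables tested together.** If drop-out is unrelated to baseline and the tests are independent, the chance of at least one significant result is 1 − 0.95^12 = 46%. By simulation, with pairwise correlations of 0 to 0.5, it is about 31–47%, the upper end matching the exact 46% within simulation error. All twelve tests are therefore null in only about 53–69% of such trials, and the check can label drop-out systematic by chance.

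**Step 4: what baseline adjustment does.** With drop-out driven by response independent of baseline, simulated bias was about 0.25–0.35 SD with or without adjustment for baseline. Adjustment reduces the standard error by a factor of about √(1 − r²), where r is the baseline–outcome correlation: √(1 − 0.25) = 0.87 at r = 0.5, and no gain at r = 0. It improves precision and leaves attrition bias where it was.

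**The case against.** The strongest reply is that nothing in section 9.6 depends on the sentence. The sensitivity and pattern-mixture analyses are promised whatever the baseline test shows, and the plan itself states that mixed models fail when drop-out is informative. Its wording claims support for randomness, not proof. Early leavers are asked for post-treatment data, the study is described as developmental, and its analyses are called preliminary. All of this stands, and it keeps the point minor. It does not make the stated inference valid.

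A second reply is that single-variable power does not describe the planned check, which looks across the baseline data. This also stands. If all 12 measures differed by 0.5 SD, an extreme case, at least one would be significant in about 57–99% of trials; a difference confined to one measure would fall between that and the single-variable figures. A reader might infer that the check gives false reassurance about 95% of the time. The plan does not support that, because the figure belongs to one variable. The correct statement is that the check can err in both directions.

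A reader might also infer that the plan ignores missing data, or deliberately restricts CAPS-5 to treatment completers. It does neither. The ANOVA has no attached rule for a missing post-treatment value, but in a preliminary plan with sensitivity work already promised that is missing detail. Likewise, the comparison by missing-data status has the limit described above only for people with no post-treatment CAPS-5; someone with other missing data but a retrieved CAPS-5 does have an outcome to compare.

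**Conclusion.** The inference in section 9.6 is wrong as written, and the point is minor. For any one baseline variable at N = 40, power at 0.5 SD is 15–33% and the 95% half-width is 0.65–1.07 SD. Across about a dozen measures, a chance finding of systematic drop-out arises in about 31–47% of trials when drop-out is unrelated to baseline. The logical limit holds at any sample size: baseline similarity cannot exclude drop-out driven by response during treatment.

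The figures rest on assumed drop-out of 10–40%, two-sided 0.05, independent participants and, for the multiple tests, 12 measures with pairwise correlation 0–0.5. The invalidity of the inference does not depend on those choices. The documents do not support the stronger conclusion that the Phase 2 results hinge on this test.

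**What to change.** 1. Delete the sentence that draws support for randomness from a null result. Report drop-out versus completer differences with 95% confidence intervals, state that they cannot establish that drop-out is random, and rest conclusions about attrition bias on the pattern-mixture and sensitivity analyses already planned.

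2. As a separate gain in precision, not a cure for attrition bias, make the comparison adjusted for baseline CAPS-5 the CAPS-5 estimate instead of an option. Include every randomised participant who has a post-treatment CAPS-5, whether or not they completed treatment, and align section 9.3 with this.

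A pre-set grid of shifts for the pattern-mixture analysis, or a joint model using the weekly PCL-5, would be optional detail and is not needed to correct this point.

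The cost is a few sentences of wording and slight programming, with no new data. The trial can no longer cite a null baseline test as reassurance, and people with no post-treatment CAPS-5 enter only through the sensitivity analyses.

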1. STUDY OBJECTIVES

1.1 Primary Objective

1. To refine an existing compassion meditation protocol for PTSD by evaluating participants' reactions to the intervention components and refining the practices to maximize engagement and induction of cognitive/emotional states that are most likely to counteract PTSD.
2. To evaluate the acceptability of and refine a likely future control condition (i.e., relaxation).
3. To evaluate the feasibility of conducting compassion meditation as an intervention for PTSD.
4. To establish preliminary estimates of effect size and other parameters to inform future efficacy studies of compassion meditation.

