9.2 Sample Size and Randomization

For Phase 1, we estimated sample size based on past experience in intervention development; we believe that we will need to run 4 CM groups to achieve Phase 1 refinements (e.g., [name], Norman, & [name], 2006). For the relaxation protocol, which was used in a prior PTSD study, we will begin with our modified version and expect 2 groups will be sufficient given the very minor modification. We will aim for a group size of 6-12, which can be recruited within the 1-month period we have allocated to recruitment before each group. Thus, we estimate that 60 people will take part in Phase 1 of the research.

In Phase 2, we will conduct a pilot study with 4 groups (2 CM and 2 relaxation groups, 6-12 in each group) to examine the feasibility of a randomized trial and response to CM. Thus, we anticipate approximately 40 participants in the second phase

Treatment Assignment Procedures

In phase 2, groups will be randomly assigned a treatment condition in a 1:1 ratio. The assessor will remain blind to these assignments; the study team will be careful not to disclose which group or therapist is seeing a given participant and participants will be asked to refrain from discussing the nature of their intervention during assessments. There is no need for breaking blind as treating clinicians will be aware of the treatment assignment.

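### The only analysis named for the Phase 2 drop-out rate is a between-arm chi-square with little power at about 20 per arm, and no drop-out rate is given a confidence interval

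*Combined protocol and SAP*

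**What the plan says.** Section 1.1 lists as a primary objective "To establish preliminary estimates of effect size and other parameters to inform future efficacy studies of compassion meditation". Section 9.6 says that effect size is not the major focus and that the analyses will concentrate on whether a larger trial is feasible. Section 6.2.5 treats early termination as an important part of that feasibility question.

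On drop-out, section 9.6 declares an interest ("We are also particularly interested in evaluation of patterns of missing data, dropout rates, distributional properties of variables, and correlations among measures") and then names one analysis of the rate: "Dropout rate will be compared between the groups using chi-square analysis". It also plans other work on drop-out: "We will test whether the drop-outs are random or systematic by comparing the drop-outs with the study completers on the baseline data", plus mixed-effects models, sensitivity analyses for informative drop-out, and pattern-mixture models. Descriptive statistics are promised for the variables in general.

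The only interval in the plan belongs to the primary-outcome effect size, which is to be read "in the context of the 95% confidence interval that surrounds it".

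On size, section 9.2 says "we anticipate approximately 40 participants in the second phase", in two CM and two relaxation groups of 6 to 12 people, and that "groups will be randomly assigned a treatment condition in a 1:1 ratio".

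**The concern.** The next trial needs to know what proportion of participants leave each arm, and how precisely this pilot has measured that. A p-value for equality of the two rates answers neither question. Section 9.6 recognises that a pilot effect size has a large standard error, and it responds with a confidence interval. The drop-out rate comes from the same small sample and gets no interval.

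Two things are at stake. The sample-size inflation for a full trial could be taken from a bare percentage with no sign of how uncertain it is. And a test that is likely to be non-significant whether or not retention differs could be taken as reassurance about CM against relaxation.

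**Working it through.** **Inputs.** From section 9.2: 4 groups of 6 to 12, so 4 × 6 = 24 to 4 × 12 = 48 people, or 12 to 24 per arm at 1:1. The stated total of about 40 fits 4 × 10 and gives about 20 per arm; no group size of 10 is stated, so the 40 is consistent with the range but not uniquely derivable from it. The documents give no significance level for this test, no power and no expected drop-out rate. I assume two-sided 0.05, the uncorrected Pearson statistic, and a range of drop-out rates.

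**Power.** For n per arm and drop-out counts a and b, the statistic is ((a - b)/n)² / [p(1 - p)(2/n)], with p = (a + b)/(2n). Power is the sum of Binomial(n, p1) × Binomial(n, p2) probabilities over all tables where the statistic exceeds 1.96².

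| Assumed true drop-out | 12 per arm | 20 per arm | 24 per arm |
|---|---|---|---|
| 15% v 30% | 12% | 20% | 25% |
| 20% v 40% | 18% | 29% | 33% |
| 30% v 60% | 36% | 46% | 59% |

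At 20 per arm the chance of a non-significant result is 100% minus these figures: 80%, 71% and 54%. With a continuity correction, power at 20 per arm falls to 11.5% in the first row and 17.6% in the second. The smallest significant splits at 20 per arm, uncorrected, are 0 v 4, 1 v 6, 2 v 8, 3 v 9 and 4 v 10.

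**What the planned output would hide.** Take a hypothetical result of 3/20 in one arm and 6/20 in the other.

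- Chi-square: 0.15² / (0.225 × 0.775 × 0.1) = 1.29, p = 0.26.
- Wilson 95% CIs by arm: 15% (5% to 36%) and 30% (15% to 52%).
- Newcombe 95% CI for the 15-point difference: lower limit 0.15 - √[(0.300 - 0.145)² + (0.360 - 0.150)²] = -0.11; upper limit 0.15 + √[(0.519 - 0.300)² + (0.150 - 0.052)²] = 0.39. So -11 to 39 points.
- Overall, 9/40 = 22.5%. Wilson centre (0.225 + 3.84/80)/(1 + 3.84/40) = 0.249; half-width 0.126; 95% CI 12% to 38%.
- Inflation factor 1/(1 - d): 1/(1 - 0.123) = 1.14 to 1/(1 - 0.375) = 1.60.

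The p-value of 0.26 conveys none of this spread.

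**Clustering.** Section 9.2 assigns whole therapy groups, two per arm. The chi-square and the intervals above treat participants as independent. With an assumed intraclass correlation of 0.05 and 10 per group, the design effect is 1 + 9 × 0.05 = 1.45, so 20 per arm carries the information of about 20/1.45 = 14. The intervals above are therefore probably too narrow.

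**The case against.** The best defence is that little is actually lost. A chi-square needs the counts by arm, descriptive statistics are planned, and anyone with n/N can compute an interval. Drop-out is not a listed Phase 2 outcome in section 9.5. Phase 1 adds about 60 people, with attendance among its primary outcomes and high drop-out as a trigger for refinement (section 5.1). Section 9.6 already calls all analyses preliminary. This stands as far as it goes: the gap is one of stated analysis and reporting, not of data or design. But a general caution is not an interval, and Phase 1 is nonrandomized with a protocol that changes between groups.

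Three stronger readings are tempting, and the documents do not support them.

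- *Drop-out is analysed by nothing but the chi-square.* Section 9.6 plans several other drop-out analyses. They address who leaves and what bias results; none estimates the rate.
- *The test cannot detect a doubling, so non-significance is all but certain.* Power of 20% to 46% at 20 per arm is low but not nil, and it reaches 59% for 30% v 60% at the largest permitted arm size.
- *The plan will take a non-significant result as equal retention.* It does not say so. Section 9.6 does treat an absence of significant differences as support for random drop-out, but that concerns drop-outs against completers at baseline. The risk of a similar reading here is an inference.

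**Conclusion.** The point holds as a cheap improvement to the analysis plan. The drop-out rate, which the plan's own objectives make a feasibility parameter, is assigned a comparison that at about 20 per arm will probably be non-significant even if one arm loses twice as many people, and it is assigned no measure of precision. In the worked example the planning uncertainty is an inflation factor anywhere from 1.14 to 1.60, before any allowance for clustering.

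The size rests on assumed drop-out rates, two-sided 0.05, an uncorrected test and 20 per arm. Other plausible rates change the figures, but power stays below 50% at 20 per arm for each doubling shown. The trial's data, design and primary result are unaffected.

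**What to change.** In section 9.6, replace the chi-square sentence with:

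> Drop-out will be reported overall and by arm as n/N with a Wilson 95% CI, the CM minus relaxation difference with a Newcombe 95% CI, and counts for each of the four therapy groups. Because whole groups are assigned, these intervals ignore clustering and may be too narrow. No conclusion of similar retention will be drawn from a non-significant test.

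How the next trial uses the interval to inflate its sample can be left to that trial's planners. The cost is this short statement and a few extra table columns, with no new data. The downside is that reported retention will look less certain, which reflects what the data can support.
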